7.1.2 Secondary Effectiveness Endpoints

[figure not shown]
If not otherwise specified, analyses of secondary endpoints will be based on OC for the ITT and the PP subset.

- The FACE-Q satisfaction with eyes sum scores and the Rasch-transformed scores ranging from 0 to 100 will be summarized by treatment arm (i.e. treatment and control) using descriptive statistics for baseline and Month 2 and change from

baseline. The two-sided 95% for the mean (assuming normal distribution) will be provided in addition. The single questions will not be summarized. The Rasch-transformed scores are computed as sum scores from the responses to the separate items and then converting the sum scores to a scale from 0 to 100.

Higher scores reflect a better outcome. If missing data is less than 50% of the scale's items, the rounded mean of the completed items will be inserted for any missing item. If missing data is 50% or more of the scale, the sum score will be set to missing. This will be done for the sum of untransformed scores. [REDACTED]

[REDACTED]

[figure not shown]
- The GAIS at Month 2 completed by investigator and subject will be summarized descriptively for treated subjects. In addition, the investigator and subject GAIS will be categorized in classes [REDACTED]
[REDACTED]
[REDACTED]

[figure not shown]
- The responder rates at Month 2 according to the MIHAS [REDACTED] will be summarized by treatment arm (i.e. treatment and control). Treatment response is defined as \geq 1-point improvement on both IOHs compared to baseline. A subject will be considered a responder if a treatment response of at least a 1-point change on both IOHs would be determined [REDACTED]. Additionally, the proportion of responders [REDACTED] will be computed based on the definition of treatment response detailed above. This will be summarized descriptively and by a two-sided 95% Newcombe confidence interval for the risk differences.

[figure not shown]
The original MIHAS results of both IOHs [REDACTED] will be further presented descriptively in frequency tables for baseline and Month 2 whereby MIHAS [REDACTED] and the median MIHAS will be tabulated.

Moreover, all secondary effectiveness endpoints will be summarized for the following subgroups:

- Fitzpatrick Skin Types (I, II, III versus IV, V, VI)
- Gender

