2.1.1 Effectiveness

[figure not shown]
The effectiveness and relevance of aesthetically pleasing outcomes following Belotero Balance injection will be established in the following manner:

- The primary endpoint (see [Section 2.2.1](#)) will establish effectiveness by using the MIHAS to demonstrate that clinically relevant changes of ≥ 1 -point on both IOHs can be detected 2-months post-treatment.
- The secondary endpoints (See [Section 2.2.2](#)) including the validated FACE-Q satisfaction with eyes, the investigator GAIS, and the subject GAIS will be utilized to substantiate aesthetically pleasing outcomes. The GAIS assessments will be used in the treated subjects only. Improvements in the FACE-Q satisfaction with eyes scores from baseline to 2-months post-treatment will indicate that subjects are satisfied with treatment effects observed on their IOHs and such changes are considered to be clinically relevant from the subject's perspective. Responses for FACE-Q satisfaction with eye scores in the control group will be compared to that of the treatment group in order to show that changes in satisfaction post-treatment are clinically relevant to the subject.

Additionally, the investigator and subject GAIS scores at Month 2 post last injection will be utilized to demonstrate the level of improvement, when compared to baseline photographs, resulting from treatment in the IOHs.

- The level of agreement in treated subjects between the MIHAS responders (≥ 1 -point improvement on both IOHs), [REDACTED] and the level of improvement (score of ≥ 1) on the treating investigator- and subject-GAIS assessments will be obtained. Aesthetically pleasing outcomes that are clinically relevant will be established if the agreement between the MIHAS responders and the level of improvement on the investigator- and subject-GAIS scores, respectively, are met as per the pre-defined endpoints in [Section 2.2.3](#).

In totality, the results from the MIHAS, as well as the supportive outcomes obtained from the treating investigator and subject perspectives regarding aesthetic improvements, will be used to establish that Belotero Balance injections in the IOH region are effective in producing clinically relevant and aesthetically pleasing outcomes.

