2.2.2 Secondary endpoints

- Summary of the FACE-Q satisfaction with eyes scores for treated subjects at baseline and Month 2 post last injection (i.e., either baseline treatment or touch-up, if applicable) and for control subjects at baseline and Month 2. The subject's assessment is based on taking into consideration both eyes.
- Descriptive summary of GAIS scores for treated subjects at Month 2 post last injection (i.e., either baseline treatment or touch-up, if applicable), as completed by the treating investigator. This assessment is a measure of aesthetic improvement relative to the baseline pre-treatment condition, as assessed from photographs.
- Descriptive summary of GAIS scores for treated subjects at Month 2 post last injection (i.e., either baseline treatment or touch-up, if applicable), as completed by the subject. This assessment is a measure of aesthetic improvement relative to the baseline pre-treatment condition, as assessed from photographs.
- Summary of the responder rates in the treatment group and the control group at Month 2, according to the MIHAS, [REDACTED] using subject photographs. In addition to baseline photograph assessments, for subjects randomized to treatment, if no touch-up is performed, the photographs assessed will be those taken at 2-months post baseline injection. If a touch-up is performed, the photographs assessed will be those taken at 2-months post touch-up. For subjects randomized to the untreated control group, the photographs assessed will be taken at 2-months from the baseline visit.

Treatment response is defined as \geq 1-point improvement on both IOHs when comparing the change from baseline to Month 2. A subject will be considered a responder if a treatment response of at least 1-point change on both IOHs is determined [REDACTED].

2.2.4 *Safety endpoints*

- Incidence and nature of device- and/or injection-related AEs and SAEs observed during the study.
- Incidence, severity, and duration of pre-specified CTRs reported in subject diaries.

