8.4.1.2 Secondary effectiveness endpoint

[figure not shown]
- For the FACE-Q satisfaction with eyes, sum scores and the equivalent Rasch-transformed scores will be analyzed descriptively for baseline and Month 2 for treatment and control groups. The FACE-Q scale will be scored using a look-up conversion table approach. The scale ranges from 0 to 100 with higher numbers indicating greater satisfaction. The FACE-Q user manual is included in [Appendix 10.4](#), and additional information related to the scoring of the FACE-Q satisfaction with eyes scale will be included in the SAP.
- The investigator GAIS categories will be analyzed descriptively at Month 2 post last injection (i.e., either baseline treatment or touch-up, if applicable) among treated subjects using counts (n) and percentages (%) for each GAIS category

- The responder rates at Month 2 according to the MIHAS, [REDACTED] using subject photographs will be summarized. Treatment response is defined as \geq 1-point improvement on both IOHs compared to baseline.

[figure not shown]

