6.1.2 Secondary Endpoints

- Summary of the FACE-Q satisfaction with eyes scores for treated and control subjects at baseline and Month 2. The subject's assessment is based on taking into consideration both eyes.
- Descriptive summary of GAIS scores for treated subjects at Month 2, as completed by the treating investigator. [REDACTED]
[REDACTED]
- Descriptive summary of GAIS scores for treated subjects at Month 2, as completed by the subject. [REDACTED]
[REDACTED]
- Summary of the responder rates in the treatment group and the control group at Month 2, according to the MIHAS [REDACTED]
[REDACTED].

Treatment response is defined as \geq 1-point improvement on both IOHs when comparing the change from baseline to Month 2. A subject will be considered a responder if a treatment response of at least 1-point change on both IOHs is determined [REDACTED]
[REDACTED].

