7.1 Effectiveness Endpoints

The primary efficacy analysis and all secondary endpoints will be based primarily on the ITT and additionally, for sensitivity purposes, on the PP. [REDACTED]

Statistical tests will be two-sided hypothesis tests for between-treatment arm differences in general. Continuous variables (values and changes from baseline) will be summarized by number of observed values (n obs), number of missing values (n miss)/ number of imputed values (n imp), mean, standard deviation (SD), median, minimum, and maximum. For qualitative variables, absolute and percent frequencies (n, %) including the number of missing values and, if applicable, shift tables also including the number of missing values will be displayed. Confidence limits and descriptive p-values will be given, where appropriate.

P-values will be reported to four decimal places (e.g., p=0.0375). P-values below 0.0001 will be presented as '<0.0001'.

Mean, median will be reported to one decimal place more than the data were collected, for the standard deviation two decimal places more will be displayed; for derived data, an adequate number of decimal places will be chosen. Percentages will be calculated using the denominator of all subjects in a specified population, or treatment arm. The denominator will be specified in a footnote to the tables for clarification if necessary. Percentages will be reported to one decimal place.

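### The protocol promises a treatment-versus-control comparison of FACE-Q satisfaction with eyes, but the public analysis text names no between-arm estimate; one descriptive adjusted difference would supply it at little cost

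*SAP*

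**What the plan says.** Protocol section 2.1.1 announces a comparison: "Responses for FACE-Q satisfaction with eye scores in the control group will be compared to that of the treatment group". The purpose given there is to show that changes in satisfaction matter to the subject. The preceding sentence also points to change from baseline: "Improvements in the FACE-Q satisfaction with eyes scores from baseline to 2-months post-treatment will indicate that subjects are satisfied".

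The endpoint and analysis sections are narrower:

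- Protocol 2.2.2: "Summary of the FACE-Q satisfaction with eyes scores for treated subjects at baseline and Month 2 post last injection", with a parallel summary for controls.
- Protocol 8.4.1.2: FACE-Q scores "will be analyzed descriptively for baseline and Month 2 for treatment and control groups".
- SAP 6.1.2: "Summary of the FACE-Q satisfaction with eyes scores for treated and control subjects at baseline and Month 2".
- SAP 7.1.2: descriptive statistics by arm for baseline, Month 2 and change, and then "The two-sided 95% for the mean (assuming normal distribution) will be provided in addition". The noun after the percentage is missing; a confidence interval is presumably meant.

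SAP 7.1 holds two general rules: "Statistical tests will be two-sided hypothesis tests for between-treatment arm differences in general" and "Confidence limits and descriptive p-values will be given, where appropriate". Neither mentions FACE-Q. For the secondary MIHAS responder rate, SAP 7.1.2 does name a between-arm estimate, a Newcombe 95% interval for the risk difference.

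**The concern.** The one secondary endpoint for which section 2.1.1 expressly announces a between-arm comparison has no between-arm estimate in the visible text. The general rules in SAP 7.1 permit one, but leave open whether it would use Month 2 scores, change scores or baseline-adjusted scores.

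GAIS is completed for treated subjects only. Among the visible secondary endpoints, FACE-Q satisfaction with eyes is therefore the patient-reported one with a randomised control. The pilot is meant to inform a pivotal study, whose designer would want a difference, its interval and a residual SD. Without a named estimate, readers must compare two arm-wise intervals or assemble the difference themselves.

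**Working it through.** **The plan's own figures.** The documents give no power or precision for FACE-Q. Their figures, about 80% with 40 and 20 subjects and about 84% with 44 and 22, concern the primary MIHAS comparison. Exact Fisher power at one-sided 0.025, for 0.60 against 0.20, is 79.1% and 84.8%, so those figures stand.

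**Inputs.** Group sizes 44/22 enrolled and 40/20 evaluable (Protocol 8.1, SAP 4). Three sites, with randomisation stratified by site (Protocol 8.2, SAP 4.1). The baseline FACE-Q form precedes randomisation in the visit order (Protocol 5.1), so it is a valid covariate. The baseline-to-Month 2 correlation ρ is not given; I assume 0.3, 0.5 and 0.7. Working in SD units avoids assuming a value for the SD, but it does assume a common one.

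**Formula.** Half-width = t(0.975, df) × √(1/n₁ + 1/n₂) × k, where

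- Month 2 alone: k = 1, df = N − 2
- change score: k = √(2(1 − ρ)), df = N − 2
- ANCOVA with baseline and site: k = √(1 − ρ²), df = N − 5 (intercept, arm, baseline, two site terms)

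For 44/22, √(1/44 + 1/22) = 0.2611, t(64) = 1.998 and t(61) = 2.000. At ρ = 0.5:

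- Month 2 alone: 1.998 × 0.2611 = 0.522
- change score: 0.522 × √1 = 0.522
- ANCOVA: 2.000 × 0.2611 × √0.75 = 0.452

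| Half-width (SD units) | ρ = 0.3 | ρ = 0.5 | ρ = 0.7 |
|---|---|---|---|
| 44/22, ANCOVA | 0.498 | 0.452 | 0.373 |
| 44/22, change score | 0.617 | 0.522 | 0.404 |
| 44/22, Month 2 alone | 0.522 | 0.522 | 0.522 |
| 40/20, ANCOVA | 0.524 | 0.475 | 0.392 |
| 40/20, change score | 0.649 | 0.548 | 0.425 |
| 40/20, Month 2 alone | 0.548 | 0.548 | 0.548 |

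At 44/22 the model-based ANCOVA interval is 19%, 13% and 8% narrower than the change score, and 4.5%, 13% and 28.5% narrower than Month 2 alone.

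**Arm-wise intervals as a substitute.** For Month 2 means at 44/22, the half-widths are t(43)/√44 = 0.304 SD and t(21)/√22 = 0.443 SD. Judging by non-overlap would need a gap of 0.304 + 0.443 = 0.747 SD, well above the 0.522 SD half-width of the difference itself.

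**Unequal variances.** The table assumes equal variances. Only one arm is treated and allocation is 2:1, so I simulated the ANCOVA at 44/22 with ρ = 0.5. The ratios of residual SDs are assumptions.

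- Control 1.25 times treated: the ordinary 95% interval covers about 93 to 94%.
- Control 1.5 times treated: about 91 to 92%.
- Treated 1.5 times control: about 97%, that is, too wide.

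HC3 standard errors bring coverage to about 95 to 96%. Their price under equal variances is an interval about 4% wider: 0.452 × 1.04 = 0.470 SD, still 10% below 0.522. If the same 4% held at the other correlations, which was not checked, the half-widths would be 0.498 × 1.04 = 0.518 and 0.373 × 1.04 = 0.388. The gain over Month 2 alone would then almost vanish at ρ = 0.3, and the gain over the change score would shrink to about 4% at ρ = 0.7.

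**Timing.** A touched-up subject is injected again at Day 28 and assessed 56 days later, nominally at Day 84 from baseline. Controls are assessed at Day 56.

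**The case against.** Comparing need not mean testing or modelling. Two arms set side by side, with change from baseline and intervals, arguably satisfy section 2.1.1, and the protocol itself calls the FACE-Q analysis descriptive. This stands: a reader might infer that the protocol and SAP contradict each other, and the documents do not support that.

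A reader might also infer that the sponsor planned no contrast. The public text cannot show this. SAP 3.2.1, 7.1 and 7.1.2 and Protocol 3.2.1.5 contain redactions, and Protocol 2.2.3 and 8.4.1.3 and SAP 7.3 are not visible. The point is limited to what can be read.

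Nor is information lost. The planned n, means and SDs yield the unadjusted difference. With the same subjects at both visits they also yield the baseline-adjusted one without site, because the within-arm covariance is (SD²baseline + SD²Month 2 − SD²change)/2. If 10% of Month 2 scores are missing at random (44/22 falling to 40/20), the rebuilt value is off by only 0.020, 0.032 or 0.046 SD on average at the three correlations. What remains is that a reader's reconstruction is not a pre-specified, reported estimate, and it omits the randomisation stratum.

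Finally, the precision gain rests on assumed correlations, and an equal-variance ANCOVA has its own weakness at 2:1. Both are fair. The second is why robust errors belong in the proposal.

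**Conclusion.** The point holds as a low-severity improvement, confined to the public text. A between-arm FACE-Q comparison is announced and permitted, but no estimate is named. Naming one would settle the choice of contrast in advance.

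The expected model-based half-width at 44/22 is about 0.50, 0.45 or 0.37 SD, against 0.62, 0.52 or 0.40 for the change score and 0.52 for Month 2 alone. This rests on equal variances and assumed correlations of 0.3, 0.5 and 0.7. The robust interval, checked at 0.5, is about 4% wider when variances are equal.

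It would be wrong to read the adjusted difference as a clean device effect. Subjects report on themselves and controls are untreated, so expectation enters the contrast and adjustment does not remove it. The Month 2 clock also differs for touched-up subjects. No stated figure is wrong, and the primary MIHAS conclusion does not depend on this.

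**What to change.** First confirm whether a FACE-Q contrast already stands in the redacted text. If not, add to SAP 7.1.2 one descriptive ANCOVA:

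- Population: ITT, observed cases with both scores.
- Model: Month 2 Rasch-transformed satisfaction-with-eyes score on arm, baseline score and site.
- Report: adjusted mean difference, its two-sided 95% confidence interval with heteroscedasticity-robust standard errors (for example HC3), and the residual SD by arm. No hypothesis test.

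Keep the arm-wise summaries, and complete the sentence on the 95% interval. State that this is the comparison meant in Protocol 2.1.1, that the outcome is self-reported against an untreated control, and that Month 2 runs from the last injection (touch-up if given) in treated subjects but from baseline in controls.

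The cost is one model, one table row and a slightly wider interval from the robust errors. The data are already collected in both arms; no subjects, visits or alpha are added.

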7.2 Safety Endpoints

All safety analyses will be performed on the SP. Summary tables will be stratified by actual treatment received and not by randomized treatment arm.

Adverse events

All AEs will be coded according to the Medical Dictionary for Regulatory Activities (MedDRA) version in effect at the time the database is closed.

TEAEs are defined in the following way:

- Treated subjects: all AEs with onset or worsening at or after the first administration of study treatment
- Not treated subjects: all documented AEs.

For treated subjects, TEAEs will be allocated to two different periods:

- Period 1: AEs with onset or worsening on or after date and time of the first administration of study treatment and up to Month 2 visit.
- Period 2: AEs with onset or worsening after Month 2 visit.

All analysis will be performed by period and overall, whereby only analysis for period 1 will be stratified by actual treatment arm. For the interim analysis, only time period 1 will be analyzed. Based on the exact number of TEAEs that will be documented in period 2, some of the summary tables may be omitted. A separate listing that contains only TEAEs of period 2 will be added.

An overall summary of AEs will be provided for the following, any line that is not applicable may be deleted in the final table:

- Any AEs

- Any non-TEAEs (for treated subjects)
- Any TEAEs
- Any treatment-related TEAEs (for treated subjects)
- Any serious TEAEs
- Any serious treatment-related TEAE (for treated subjects)
- Any TEAEs leading to discontinuation
- Any treatment-related TEAEs leading to discontinuation (for treated subjects)
- Any fatal TEAEs
- Any treatment-related fatal TEAEs (for treated subjects)

Incidences will be provided for the following classes of AEs:

- TEAEs, subjects with TEAEs and number of TEAEs by system organ class (SOC) and preferred term (PT)
- TEAEs, subjects with TEAEs by PT
- TEAEs by worst intensity, subjects with TEAEs by PT
- Related TEAEs by worst intensity, subjects with TEAEs by PT
- TEAEs by worst causal relationship, subjects with TEAEs by PT
- TEAEs by worst outcome, subjects with TEAEs by PT
- TEAEs by maximum duration, subjects with TEAEs by PT (1-3 days, 4-7 days, 8-14 days, ≥ 15 days)
- Treatment related TEAEs, subjects with TEAEs and number of TEAEs by SOC and PT
- TESAEs, listing of subjects (in case of more than 15 TESAEs respective table by SOC and PT will be provided)
- Deaths, listing of all serious TEAEs leading to death
- TEAEs leading to discontinuation, listing of subjects.

[figure not shown]
The duration of AEs will calculated by the difference of start and stop day plus 1.

[figure not shown]
If a subject has more than one outcome within a preferred term (PT) only the worst outcome in respective time period will be used in the frequency tables. Also on subject level only the worst outcome category per subject in respective time period will be counted in the frequency table. The worst outcome is defined in the following order:

- recovered/resolved
- recovered/resolved with sequelae
- recovering/resolving
- not recovered/not resolved
- unknown
- fatal

[figure not shown]
Moreover, incidences of TEAEs (PT and SOC) and of related TEAEs (PT and SOC) will be provided for the following subgroups:

- Fitzpatrick Skin Types (I, II, III versus IV, V, VI)
- Gender

Urine pregnancy tests, visual safety assessments and device deficiencies will only be listed.

[figure not shown]

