NOTE: This phone call is only for subjects assigned to the treatment group.

- Review and record changes in concomitant medications/therapies. Confirm subject remains compliant with any applicable study restrictions (see [Section 4.4](#)).
- Review and record AEs. Site staff will review subject diary responses to identify any safety concerns.

- If subject reports a safety concern, the subjects will be scheduled for an unscheduled visit, referred to a specialist, or be provided means of emergency medical care as determined by the investigator.
- Remind subject to continue the diary.
- Schedule and/or confirm Week 2 visit.

Week 2: Day 14 (+3 days)

NOTE: This visit is only for subjects assigned to the treatment group.

- Review and record changes in concomitant medications/therapies. Confirm subject remains compliant with any applicable study restrictions.
- Review subject diary for potential AEs. Remind subject to continue to record in the diary until Month 1 visit.
- Review and record AEs.
- Take standardized IOH photographs.
- Visual Safety Assessments on both eyes.
 - Visual acuity test (using a Snellen chart);
 - Visual field test;
 - Ocular motility exam; and
 - Fundoscopic (ophthalmoscopic) view of the eye (not dilated).
- Schedule and/or confirm Month 1 visit.

Month 1: Day 28 (+3 days) Safety and assessment for Touch-up (TU)

NOTE: This visit is only for treated subjects

- Review and record changes in concomitant medications/therapies. Confirm subject remains compliant with any applicable study restrictions.
- Take standardized IOH photographs.
- Review and collect subject diary. The investigator will review the diary and determine if any diary entries should be recorded as AEs on the AE eCRF.
- Visual Safety Assessments on both eyes.
 - Visual acuity test (using a Snellen chart);
 - Visual field test;

[figure not shown]
- Ocular motility exam; and
- Fundoscopic (ophthalmoscopic) view of the eye (not dilated).
- Review and record AEs.
- Schedule and/or confirm Month 2 visit.
- Asymmetry assessment based on a visual assessment completed by the treating investigator.

NOTE: Subjects who don't receive a touch up to address asymmetry based on the treating investigator's assessment have completed this visit and will be scheduled for the Month 2 visit.

Month 1: Touch-up (TU)

If the treating investigator determines a touch-up is needed to address asymmetry the following procedures will be done:

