- Perform urine pregnancy test (if female of childbearing potential and for treated subjects only). Negative test required prior to touch-up injection.
- Injection (only if treating investigator notes asymmetry):
 - Administer touch-up injection **to first IOH.**

- Wait 30 minutes.
- Perform visual safety assessments on first eye (where IOH area was treated).
- Administer treatment injection to second IOH if treating investigator agrees that it is safe to proceed with injecting the second IOH.
- Wait 30 minutes.
- Perform visual safety assessments on other eye (where second IOH area was treated).

NOTE: If only injecting one side, only the side being injected will need the visual safety assessment 30 minutes post treatment.

- Dispense subject diary and discuss completion instructions.

- Review and record AEs.
- Schedule 72-hour follow-up phone call and Week 2 visit.

NOTE: For subjects receiving a touch-up refer to the Follow-up 72 hour Phone Call, Week 2 and Month 1 (safety) assessments as described above. Then subject will continue with Month 2 assessments.

Month 2: Day 56 (+3 days) ALL SUBJECTS

Visit to occur 2 months after last injection (either baseline treatment or touch-up, if applicable) or 2 month after baseline visit for control subjects.

- Review and record changes in concomitant medications/therapies. Confirm subject remains compliant with any applicable study restrictions.
- Perform urine pregnancy test (if female of childbearing potential and for treated subjects only).
- Take standardized IOH photographs.
- Collect weight.
- Review and collect subject diary (touch-up subjects only). The investigator will review the diary and determine if any entries should also be recorded as AEs on the AE eCRF.
- Visual Safety Assessments on both eyes.
 - Visual acuity test (using a Snellen chart);
 - Visual field test;
 - Ocular motility exam; and
 - Fundoscopic (ophthalmoscopic) view of the eye (not dilated).
- [REDACTED] perform MIHAS assessment.

[figure not shown]
- Have the treating investigator complete the investigator GAIS (treated subjects only).

NOTE: Standardized photographs, previously taken during the baseline visit, will be available for the treating investigator to reference when completing the Month 2 GAIS assessment.

- Have subjects complete the subject GAIS (treated subjects only).

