7 STATISTICAL ANALYSIS METHODS

The sponsor will finalize the formal SAP prior to database lock. Deviations from the analyses outlined in the study protocol are documented in this SAP.

Adequate descriptive statistics will be provided for each endpoint. Continuous variables will be summarized by number of observations, number of missing or number of imputed observations, mean, standard deviation, minimum, median, and maximum. Categorical data will be summarized in frequency tables using counts (n) and percentages (%). Ordered categorical data will be summarized by both.

If not otherwise specified Month 2 data refers to

- Month 2 post last injection visit (i.e., either baseline treatment or touch-up, if applicable) for subjects in the treatment group and
- Month 2 post baseline visit for subjects in the control group.

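### The only adverse-event period tabulated by arm runs to about Day 84 for touch-up subjects but to Day 56 for controls (minor; descriptive all-cause TEAE tables only)

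*SAP*

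**What the plan says.** SAP 7.2 allocates the TEAEs of treated subjects to two periods. Period 1 covers "AEs with onset or worsening on or after date and time of the first administration of study treatment and up to Month 2 visit", and Period 2 covers what follows. It adds that "only analysis for period 1 will be stratified by actual treatment arm". For controls the TEAE definition reads "Not treated subjects: all documented AEs", with no period attached.

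SAP 7.2 does not say which Month 2 visit it means, so the default in SAP 7 applies. In the treated arm this is "Month 2 post last injection visit (i.e., either baseline treatment or touch-up, if applicable) for subjects in the treatment group". The untreated arm has a different anchor, namely baseline: "Month 2 post baseline visit for subjects in the control group".

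Protocol 5.1 supplies the days. The touch-up assessment is at Day 28 (+3). The later visit is headed "Month 2: Day 56 (+3 days) ALL SUBJECTS", and is timed from the last injection, or from baseline for controls, for whom it is the last visit. SAP 3.1 and Protocol 3.1 both say that a touch-up restarts the visit schedule.

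**The concern.** A side-by-side count of subjects with at least one event is easiest to read when both arms are counted over the same time. Here part of the treated arm is counted for about half as long again as the controls. Some of any difference in all-cause TEAEs can then come from longer counting alone.

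The tables concerned are those that set treated subjects beside controls for all TEAEs: the overall summary lines that are not limited to treated subjects, and the breakdowns by system organ class and preferred term, intensity, outcome and duration. The pilot is meant to inform a pivotal study (Protocol 2.1), so a reader may well take a background rate or an arm difference from them.

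**Working it through.** **Check of the calendar against the protocol's own figure.** Protocol 5.1 puts Month 12 at Day 336, which implies 28-day months. Without a touch-up, follow-up is 336/28 = 12 months. With a touch-up at Day 28 it is (28 + 336)/28 = 13 months. These match the 12 and 13 months in Protocol 3.2.2.1 and 3.2.3.3.

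**End of the counting window, in days from baseline.**

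| Group | Nominal | Latest allowed |
|---|---|---|
| Control | 56 | 59 |
| Treated, no touch-up | 56 | 59 |
| Treated, touch-up | 28 + 56 = 84 | 31 + 59 = 90 |

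The nominal ratio is 84/56 = 1.5, or 28 extra days. With touch-up share q, the mean treated window is 56 + 28q days: 58.8, 63 and 70 for q = 10%, 25% and 50%.

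**Size of the effect.** The documents give neither a background event rate nor a touch-up share. Assume no device effect, a constant background rate with incidence p per 56 days, and q of 10%, 25% or 50% of the 44 planned treated subjects.

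- Touch-up subject over 84 days: 1 − (1 − p)^(84/56). This is 0.1462 for p = 0.10 and 0.2845 for p = 0.20.
- Treated arm: (1 − q)p + q[1 − (1 − p)^1.5].

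| p | q | Treated arm | Added points | Added subjects (of 44) |
|---|---|---|---|---|
| 10% | 10% | 10.46% | 0.46 | 0.20 |
| 10% | 25% | 11.15% | 1.15 | 0.51 |
| 10% | 50% | 12.31% | 2.31 | 1.02 |
| 20% | 10% | 20.84% | 0.84 | 0.37 |
| 20% | 25% | 22.11% | 2.11 | 0.93 |
| 20% | 50% | 24.22% | 4.22 | 1.86 |

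**All visits at the latest allowed day, p = 20%.** Over 90 days: 1 − 0.8^(90/56) = 0.3014. Over 59 days: 1 − 0.8^(59/56) = 0.2095. The difference is 0.0919. Multiplied by q = 10%, 25% and 50%, it gives 0.9, 2.3 and 4.6 points.

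**Against sampling error.** With 44 and 22 subjects and 20% in each arm, the standard error of the difference is √(0.16/44 + 0.16/22) = 0.1044, so the 95% half-width is 1.96 × 0.1044 = 20.5 points. At p = 20% the nominal shift is 0.84/20.5 = 4% to 4.22/20.5 = 21% of that half-width.

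**The case against.** The best defence is that the window is deliberate. The touch-up is part of the assigned strategy, the Month 2 report is itself cut at Month 2 after the last injection (SAP 7.4.2), and stopping at Day 56 would discard events in the second month after a repeat injection. For describing the device this is sound, and it is why the Period 1 tables should stay. It does not make the control column comparable.

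It can also be said that little depends on these tables. No test of adverse events is planned, the endpoints in SAP 6.2 are related events and diary responses, and the treatment-related summary lines are limited to treated subjects. This stands and keeps the point minor. So does the remark that the 50% touch-up share has no support in the documents: touch-ups are only for investigator-judged asymmetry, in subjects whose two sides score equally at entry.

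The most serious objection is that equal windows do not give equal ascertainment. Treated subjects have a diary, a phone call and extra visits. Controls have no diary and one follow-up visit (Protocol 3.1 and 3.2.2.1). A matched table removes only the difference in counting time, and must say so.

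Three stronger readings are tempting.

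- A reader might infer that the safety conclusions are biased against the device. The documents do not support this: the stated endpoints do not rest on the arm contrast, and events that follow a second injection can be real consequences of the strategy.
- A reader might infer that the window starts also differ materially, because control events are counted from consent (Protocol 7.2.4.1) and treated events from first injection. Protocol 3.2.3.3 places screening, randomisation and treatment at one visit, and only the 28-day allowance in the baseline visit heading of Protocol 5.1 hints otherwise. The gap is probably near zero.
- A reader might infer that no common-window table is planned at all. Parts of SAP 7.2, the text between SAP 7.2 and 7.4, and the sponsor's standard table set are not visible, so this cannot be established. Listings by actual arm are planned and onset dates are collected, so later events may be identifiable there.

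**Conclusion.** The point holds as a minor one. The difference in window length follows directly from SAP 7, SAP 7.2 and Protocol 5.1. SAP 7.2 assigns no period to controls, but their observation stops at Day 56 (+3) because that is their last visit.

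The nominal shift in the treated arm is about 0.5 to 4.2 percentage points, or 0.2 to 1.9 subjects; with every visit at its latest day and 20% background it is 0.9 to 4.6 points. These sizes rest on assumed background rates and touch-up shares, a constant rate, and equal ascertainment in the two arms, which this trial does not have. They illustrate the effect of counting time and do not predict the observed difference. Confidence is high on the timing and moderate on the absence of a common-window table.

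**What to change.** In SAP 7.2, keep the full Period 1 tables and add one supplementary by-arm table of all-cause TEAEs with a single cut date. Count onset or worsening from first injection (treated) or randomisation (control) through study Day 56 in every subject, with baseline as Day 0. Use Day 56 itself, because Day 56 (+3) is a visit window and would leave the cut undefined. In a footnote, give the number of touch-up subjects and the mean Period 1 length by arm.

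The cost is a short SAP addition and one table from dates already collected. Nothing changes in conduct, sample size or the primary analysis.

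State two limits with the table:

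- It omits touch-up subjects' events after Day 56. If the touch-up is on Day 31, its 28-day diary runs to 31 + 28 = Day 59, so up to 3 diary days are lost. The table can therefore only supplement the Period 1 tables.
- It does not equalise ascertainment between the arms.
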